1.0 BACKGROUND AND RATIONALE

1.1 Hormone Receptor Positive Breast Cancer

Hormone receptor positive (estrogen receptor (ER+) and/or progesterone receptor (PR+)) breast cancers account for nearly 80% of breast cancer diagnoses. Endocrine therapies are the cornerstone of treatment for these cancers. A meta-analysis by the Early Breast Cancer Trialists' Collaborative Group showed that these agents substantially reduce the relapse rate and mortality in the adjuvant setting for early stage breast cancers that were ER+ or PR+ (1).

In spite of advances in endocrine therapy, a considerable clinical challenge remains in the form of many women presenting with systemic relapse of breast cancer either during or after completion of adjuvant hormone therapy. In aromatase inhibitor (AI) resistant setting, hormonal therapy such as a different AI, tamoxifen or the selective estrogen-receptor down regulator fulvestrant, as single agents have shown limited clinical benefit (2-4). Although the mTOR inhibitor everolimus has shown to improve PFS in the AI resistant setting, its activity is modest and is associated with significant toxicity including mucositis and hyperglycemia (5).

Cyclin D1–CDK4–CDK6 (CDK- Cyclin dependent kinase) complex is a key downstream effector in ER+ and PR+ breast cancer and retains its function even after development of resistance to endocrine therapy (6,7). Targeting CDK4 and CDK6 is an attractive strategy to overcome this resistance.

1.2 Palbociclib (Ibrance)

Palbociclib (Ibrance, Pfizer) is a highly selective small-molecule inhibitor of CDK4 and CDK6, which can be administered orally. It results in loss of RB1 phosphorylation in vitro and leads to cell cycle arrest at the G1-S phase in ER+ breast cancer (8). While initial phase 2 studies demonstrated single agent activity in hormone receptor positive breast cancer (9), subsequent studies have reported synergistic activity with endocrine therapies in ER+/PR+ breast cancer. In preclinical studies, palbociclib was effective in both tamoxifen sensitive and resistant ER+ breast cancer cell lines (7).

An open-label randomized phase 2 study involving postmenopausal patients with newly diagnosed metastatic ER+ and human epidermal growth factor receptor (Her-2/neu) negative breast cancer (PALOMA1), showed that palbociclib in combination with letrozole was associated with significantly prolonged PFS when compared with letrozole alone (10). This resulted in an accelerated FDA approval of palbociclib for use in this specific patient population (11). In this trial, 27 patients in the palbociclib plus letrozole group (33%) had dose interruptions because of adverse events, compared with only three (4%) patients in the letrozole group. In the combination group, 37 (45%) patients required a delay in the start of a subsequent treatment cycle because of an adverse event and 33 (40%) patients had a dose reduction. In this study, 11 (13%) patients in the palbociclib plus letrozole group

and two (2%) patients in the letrozole group discontinued the study because of an adverse event. Of these discontinuations, six (7%) patients in palbociclib plus letrozole group and two (2%) patients in the letrozole group discontinued because of treatment-related adverse events.

A randomized phase 3 study to confirm the efficacy of palbociclib in combination with letrozole in this setting (PALOMA2) was recently reported at ASCO 2016 annual meeting and again demonstrated a significant improvement in progression free survival (PFS): 24.8 (22.1-NR) months in the palbociclib/letrozole arm vs 14.5 (12.9-17.1) months in the placebo/letrozole arm, HR 0.58; $p < 0.000001$ (12). Among the 444 patients treated with palbociclib and letrozole, neutropenia (any grade) occurred in 80% of patients vs. 6% in the placebo/letrozole arm. The incidence of grade 3 and 4 neutropenia in the palbociclib/letrozole arm was 56% and 10%, respectively. Grade 3 or 4 non-hematological AEs were uncommon. 9.7% of patients in the palbociclib/letrozole arm vs 5.9% in the placebo/letrozole arm discontinued treatment due to AEs (12).

Most recently, a randomized phase 3 study (PALOMA3) assessed the safety and efficacy of the combination of palbociclib and fulvestrant vs placebo and fulvestrant after disease progression after prior endocrine therapy in premenopausal and postmenopausal women with hormone receptor positive and Her-2/neu negative advanced breast cancer. In this study, premenopausal females also received goserelin for ovarian suppression. A significantly prolonged PFS was noted with the combination of palbociclib and fulvestrant compared with fulvestrant and placebo. The dosing schedule of palbociclib was 125 mg po daily for 3 weeks followed by one week off drug (13).

Similar to PALOMA2, most common hematologic adverse events reported for the palbociclib–fulvestrant group in PALOMA3 were neutropenia and leukopenia. Neutropenia (any grade) occurred in 78.8% of the patients receiving palbociclib–fulvestrant versus 3.5% in the placebo–fulvestrant group, leukopenia in 45.5% versus 4.1%, anemia in 26.1% versus 9.9%, and thrombocytopenia in 19.4% versus 0%. Grade 3 or 4 neutropenia occurred in 62.0% of the patients receiving palbociclib–fulvestrant versus 0.6% of the patients receiving placebo–fulvestrant, leukopenia in 25.2% versus 0.6%, anemia in 2.6% versus 1.7%, and thrombocytopenia in 2.3% versus 0%. The most common nonhematologic adverse events were fatigue, nausea (29.0% vs. 26.2%), and headache, all of which were more common in the palbociclib-fulvestrant group. A higher incidence of infections was also reported in the palbociclib–fulvestrant group (13).

Palbociclib dose was reduced in 109 of 345 patients (31.6%), whereas the placebo dose was reduced in 3 of 172 patients (1.7%). Discontinuation of palbociclib or matching placebo owing to adverse events occurred in 9 patients (2.6%) receiving palbociclib and 3 patients (1.7%) receiving placebo (13).

1.3 Study Rationale

The current dose modification guidelines for palbociclib are as follows:

CTCAE* grade	Dose modifications
Grade 1 or 2	No adjustment required
Grade 3	No dose adjustment is required. Consider repeating complete blood count monitoring one week later. Withhold initiation of next cycle until recovery to Grade ≤ 2
Grade 3 ANC (<1000 to 500/mm ³) + Fever ≥ 38.5 C and/or infection	Withhold Palbociclib and initiation of next cycle until recovery to Grade ≤ 2 (≥ 1000 /mm ³). Resume at next lower dose
Grade 4	Withhold Palbociclib and initiation of next cycle until recovery to Grade ≤ 2 . Resume at next lower dose

*Common terminology criteria for adverse events

We propose to conduct a study to test an alternative dosing schedule of palbociclib. With the current three-week on and one week off schedule, a significant number of patients develop grade 3 or higher degree of neutropenia and require dose reduction and sometimes discontinuation. This potentially compromises the efficacy of the drug. In addition, as the half-life of palbociclib is 27 hours, 1 week break with the standard 3 weeks on and 1 week off dosing schedule could potentially lead to recovery of Rb phosphorylation during the off week. Hence, we propose a 5 days on and 2 days off schedule each week without any weeks off drug. Although the cumulative doses each 28-day cycle is roughly the same with this schedule compared to conventional dosing, the bone marrow is not exposed to the drug continuously for 21 days and rather gets frequent breaks from therapy. We hypothesize that the 5 days on and 2 days off schedule is more tolerable with less frequent high grade neutropenia and dose interruption/reduction. In addition, this schedule also provides for a more continuous drug delivery to the patient since there is not a week's break in therapy, which could ultimately prove to be more efficacious.

1.4 Correlative Studies Background

Serum TK1 activity

Thymidine kinase-1 (TK1) is an enzyme which plays a critical role in the synthesis of DNA. All human cells express this enzyme during normal cell division through E2F-dependent transcription with only small amounts of the enzyme released into the serum (14,15). Due to higher rates of replication compared to normal tissues, tumors are capable of secreting pathologic levels of TK1 which can be detected via an ELISA assay. In patients with metastatic breast cancer, TK1 expression and activity in human serum, was predictive for therapy response and correlated with PFS and OS (16). Given that TK1 expression is E2F-dependent, we hypothesize that CDK4 inhibitors, if active in a particular tumor, would result in reduced serum TK1 activity and can be used as a potential biomarker

for the pharmacodynamics effect of CDK4/6 inhibition. We will also evaluate changes in serum TK1 activity in relation to tumor response as an exploratory endpoint in this study.

Cell-free circulating tumor DNA (ctDNA) sequencing

Plasma samples from cancer patients often carry small amounts of fragmented cell-free DNA of 160-180 base pairs, which are originated from the necrosis or apoptotic process of cancer cells. Advances in the next generation sequencing (NGS) technology and digital genomic techniques support the clinical validity of cell-free circulating DNA (ctDNA) sequencing analysis to non-invasively identify actionable genomic alterations, monitor treatment response, and investigate resistance mechanisms (17). To investigate whether ctDNA sequencing could serve as an early predictor of response and provide clues of resistance mechanisms, blood for cell free tumor DNA sequencing will be collected before, during and at the time of progression to assess changes in the mutation profile including *PIK3CA*, *RB1*, *ESR1*, *TP53* and others. These genes are chosen as *PIK3CA*, *TP53* and *ESR1* are among the most common mutations in AI resistant ER+ breast cancer (18,19) and palbociclib has shown to be effective in ER pos breast cancers that carry these mutations (20,21). However, there is limited data on whether these mutations could be used to monitor treatment response and whether mutations in these genes could be acquired or enriched during or at progression on palbociclib. It is of particular importance whether *ESR1* mutation could develop at the time of acquired treatment resistance. The results may have implications on the development of subsequent treatment strategies. *RB1* mutation has been implicated as a de novo and acquired treatment resistance mechanism to CDK4/6 inhibition (21-23), however, the incidence of *RB1* mutation after progression on palbociclib combination regimen is unknown. This trial will provide this valuable data for future studies of targeted agents aimed to treat *RB1* mutant tumors.

Tumor analysis

In addition to archival tumor specimens, in consented patients who have accessible tumors, tumor biopsies will be obtained before and/or after disease progression to examine mechanisms of intrinsic and acquired resistance mechanisms, by proteomic analysis including reverse phase protein array, immunohistochemistry of pRB, RNA expression profiling and targeted or whole exome sequencing studies depending on funding availabilities.

Patient derived xenograft (PDX)

PDX models allow the opportunity for in-depth molecular characterization of the tumor and investigation of mechanisms of response/resistance to treatments, therefore whenever possible, we will try to engraft biopsy samples to immunocompromised mice from consented patients as described in our previous publications (24).

Circulating tumor cells (CTC)

CTCs are rare events in the bloodstream, but may provide an accessible source of material for detection, characterization and monitoring of non-hematologic malignancies. Current estimates suggest that these cells are present in numbers as low as 1 to 10 in 10^9 blood cells. The majority of studies, including those in the setting of metastatic breast cancer, utilized the FDA-cleared CellSearch System for CTC enumeration, and showed the

prognostic value of CTC count in both progression free survival and overall survival (25). With the advances of technologies, we and others have developed new methods of CTC isolation that may allow for more accurate enumeration and even biochemical characterization of these cells (26,27). Recent studies have also demonstrated success in genomic, transcriptomic, and proteomic analyses in breast cancer CTCs (28,29). These data support the use of CTCs as valuable information source to non-invasively identify actionable genomic alterations, monitor treatment response, and investigate resistance mechanisms. To investigate whether CTC-based gene expression profiling could serve as an early predictor of response and provide clues of resistance mechanisms, blood will be collected before, during and at the time of progression to assess changes in the gene expression profile, including PAM50 molecular classifiers (30-32) and cell cycle genes and regulators. Very limited data exist regarding the molecular markers for predicting or monitoring treatment response and resistance to palbociclib, it has been reported that CDK4/6 inhibitor treatment shifted ER+/HER2- models from a high risk (luminal B) to a low risk (luminal A) molecular-phenotype (33). We will associate the baseline and shift of CTC-based molecular subtype with patients' clinical response. This trial will provide this valuable data for the development of non-invasive companion diagnostics or monitoring tools for patients to receive palbociclib.

2.0 OBJECTIVES

2.1 Primary Objective

To determine the rate of grade 3 or higher neutropenia in patients with hormone receptor positive breast cancer treated with palbociclib on a 5 days on/2 days off schedule within the first 29 days of treatment.

2.2 Secondary Objectives

1. To determine the rate of grade 3 or higher neutropenia in patients with hormone receptor positive breast cancer treated with palbociclib on a 5 days on/2 days off schedule during all cycles.
2. To determine the rate of palbociclib dose reduction, interruption, or discontinuation.
3. To determine the adverse events profile of palbociclib given on a 5 days on/2 days off schedule.
4. To determine the progression free survival in patients with hormone receptor positive breast cancer treated with palbociclib on a 5 days on/2 days off schedule.
5. To determine the overall response rate (CR+PR) in patients with hormone receptor positive breast cancer treated with palbociclib on a 5 days on/2 days off schedule.
6. To determine the clinical benefit rate (CR+PR+SD for at least 6 months) in patients with hormone receptor positive breast cancer treated with palbociclib on a 5 days on/2 days off schedule.

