3.0 PATIENT SELECTION

3.1 Inclusion Criteria

1. Histologically confirmed metastatic ER+ and/or PR+ and HER2- breast cancer who are candidates for palbociclib in combination with either letrozole or fulvestrant per treating physician.
2. Presence of measurable or non-measurable disease by RECIST 1.1 criteria.
3. One prior systemic therapy in the metastatic setting is allowed, but patients who have not had any prior systemic therapies in the metastatic setting are also eligible.
 - Note: patients who were started on endocrine therapy monotherapy as their 1st line or 2nd line systemic therapy in the metastatic setting for no more than 28 days and without clinical progression prior to the initiation of the study drug therapy are allowed to enroll on the study as their 1st line or 2nd line therapy, respectively.
4. At least 18 years of age.
5. ECOG performance status ≤ 2 (see Appendix A)

6. Normal bone marrow and organ function as defined below:
 - a. Absolute neutrophil count $\geq 1,500/\text{mcl}$
 - b. Platelets $\geq 100,000/\text{mcl}$
 - c. Total bilirubin $\leq \text{IULN}$ or total bilirubin $\leq 3.0 \times \text{IULN}$ with direct bilirubin within normal range in patients with documented Gilbert's syndrome
 - d. AST(SGOT)/ALT(SGPT) $\leq 1.5 \times \text{IULN}$ (up to $5 \times \text{IULN}$ in patients with liver disease)
 - e. Creatinine $\leq \text{IULN}$ OR creatinine clearance $\geq 60 \text{ mL/min/1.73 m}^2$ for patients with serum creatinine levels above institutional normal (IULN) (calculated by Creatinine Clearance Estimate by Cockcroft-Gault Equation)
7. Pre- or post-menopausal women are allowed. If pre- or peri-menopausal, concurrent ovarian suppression for pre- or peri-menopausal women is required.
8. Women of childbearing potential must agree to use adequate contraception (hormonal or barrier method of birth control, abstinence) prior to study entry and for the duration of study participation. Should a woman become pregnant or suspect she is pregnant while participating in this study, she must inform her treating physician immediately.
9. Able to swallow and retain oral medication.
10. Washout of at least 3 weeks from prior chemotherapy or targeted therapy that induces myelosuppression and recovery of treatment related adverse events to grade 1 or less, with the exception of alopecia, is required prior to the start of palbociclib.

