5.2 Evaluability

All patients who receive any study treatment are evaluable for toxicity. Patients are evaluated from first receiving study treatment until a 30-day follow up after the conclusion of treatment or death.

All patients are evaluable for disease response unless they discontinue treatment due to treatment related adverse events(s) prior to completion of a first disease assessment.

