12.2 Disease Parameters

Measurable disease: Measurable lesions are defined as those that can be accurately measured in at least one dimension (longest diameter to be recorded) as >20 mm by chest x-ray, as >10 mm with CT scan, or >10 mm with calipers by clinical exam. All tumor measurements must be recorded in millimeters (or decimal fractions of centimeters).

Malignant lymph nodes: To be considered pathologically enlarged and measurable, a lymph node must be >15 mm in short axis when assessed by CT scan (CT scan slice thickness recommended to be no greater than 5 mm). At baseline and in follow-up, only the short axis will be measured and followed.

Non-measurable disease: All other lesions (or sites of disease), including small lesions (longest diameter <10 mm or pathological lymph nodes with ≥ 10 to <15 mm short axis), are considered non-measurable disease. Bone lesions, leptomeningeal disease, ascites, pleural/pericardial effusions, lymphangitis cutis/pulmonitis, inflammatory breast disease, and abdominal masses (not followed by CT or MRI), are considered as non-measurable.

Note: Cystic lesions that meet the criteria for radiographically defined simple cysts should not be considered as malignant lesions (neither measurable nor non-measurable) since they are, by definition, simple cysts.

‘Cystic lesions’ thought to represent cystic metastases can be considered as measurable lesions, if they meet the definition of measurability described above. However, if non-cystic lesions are present in the same patient, these are preferred for selection as target lesions.

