12.4 Response Criteria

12.4.1 Evaluation of Target Lesions

Complete Response (CR): Disappearance of all target lesions. Any pathological lymph nodes (whether target or non-target) must have reduction in short axis to <10 mm.

Partial Response (PR): At least a 30% decrease in the sum of the diameters of target lesions, taking as reference the baseline sum diameters.

Progressive Disease (PD): At least a 20% increase in the sum of the diameters of target lesions, taking as reference the smallest sum on study (this includes the baseline sum if that is the smallest on study). In addition to the relative increase of 20%, the sum must also demonstrate an absolute increase of at least 5 mm. (Note: the appearance of one or more new lesions is also considered progressions).

Stable Disease (SD): Neither sufficient shrinkage to qualify for PR nor sufficient increase to qualify for PD, taking as reference the smallest sum diameters while on study.

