12.4.2 Evaluation of Non-Target Lesions

Complete Response (CR): Disappearance of all non-target lesions and normalization of tumor marker level. All lymph nodes must be non-pathological in size (<10 mm short axis).

Note: If tumor markers are initially above the upper normal limit, they must normalize for a patient to be considered in complete clinical response.

Non-CR/Non-PD: Persistence of one or more non-target lesion(s) and/or maintenance of tumor marker level above the normal limits.

Progressive Disease (PD): Appearance of one or more new lesions and/or unequivocal progression of existing non-target lesions. Unequivocal progression should not normally trump target lesion status. It must be representative of overall disease status change, not a single lesion increase.

Although a clear progression of “non-target” lesions only is exceptional, the opinion of the treating physician should prevail in such circumstances, and the progression status should be confirmed at a later time by the review panel (or Principal Investigator).

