12.4.3 Evaluation of Best Overall Response

The best overall response is the best response recorded from the start of the treatment until disease progression/recurrence (taking as reference for progressive disease the smallest measurements recorded since the treatment started). The patient's best response assignment will depend on the achievement of both measurement and confirmation criteria.

For Patients with Measurable Disease (i.e., Target Disease)

Target Lesions	Non-Target Lesions	New Lesions	Overall Response	Best Overall Response when Confirmation is Required*
CR	CR	No	CR	>4 wks. Confirmation**
CR	Non-CR/Non-PD	No	PR	>4 wks. Confirmation**
CR	Not evaluated	No	PR	
PR	Non-CR/Non-PD/not evaluated	No	PR	
SD	Non-CR/Non-PD/not evaluated	No	SD	Documented at least once >4 wks. from baseline**
PD	Any	Yes or No	PD	no prior SD, PR or CR
Any	PD***	Yes or No	PD	
Any	Any	Yes	PD	

* See RECIST 1.1 manuscript for further details on what is evidence of a new lesion. ** Only for non-randomized trials with response as primary endpoint. *** In exceptional circumstances, unequivocal progression in non-target lesions may be accepted as disease progression. Note: Patients with a global deterioration of health status requiring discontinuation of treatment without objective evidence of disease progression at that time should be reported as “symptomatic deterioration.” Every effort should be made to document the objective progression even after discontinuation of treatment.
				

For Patients with Non-Measurable Disease (i.e., Non-Target Disease)

Non-Target Lesions	New Lesions	Overall Response
CR	No	CR
Non-CR/non-PD	No	Non-CR/non-PD*
Not all evaluated	No	not evaluated
Unequivocal PD	Yes or No	PD
Any	Yes	PD

* ‘Non-CR/non-PD’ is preferred over ‘stable disease’ for non-target disease since SD is increasingly used as an endpoint for assessment of efficacy in some trials so to assign this category when no lesions can be measured is not advised
		

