12.4.4 Duration of Response

Duration of overall response: The duration of overall response is measured from the time measurement criteria are met for CR or PR (whichever is first recorded) until the first date that recurrent or progressive disease is objectively documented (taking as reference for progressive disease the smallest measurements recorded since the treatment started).

The duration of overall CR is measured from the time measurement criteria are first met for CR until the first date that progressive disease is objectively documented.

Duration of stable disease: Stable disease is measured from the start of the treatment until the criteria for progression are met, taking as reference the smallest measurements recorded since the treatment started, including the baseline measurements.

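### As written, the clinical benefit rate gives no credit to non-measurable patients who stay progression-free for six months without CR, and Section 5.2 takes early toxicity dropouts out of response evaluation

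*Combined protocol and SAP*

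**What the plan says.** **Who enters.** Section 3.1 requires "Presence of measurable or non-measurable disease by RECIST 1.1 criteria", with no cap on the non-measurable share. Section 12.2 lists as non-measurable, among others, "Bone lesions, leptomeningeal disease, ascites, pleural/pericardial effusions".

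**How response is scored.**
- Section 12.4.1 defines SD as "Neither sufficient shrinkage to qualify for PR nor sufficient increase to qualify for PD, taking as reference the smallest sum diameters while on study", which presupposes target lesions.
- Section 12.4.2 gives non-target lesions a middle category, Non-CR/Non-PD: "Persistence of one or more non-target lesion(s) and/or maintenance of tumor marker level above the normal limits".
- The Section 12.4.3 table for patients with non-measurable disease offers CR, Non-CR/non-PD, not evaluated or PD. Its footnote prefers Non-CR/non-PD to SD and adds that "to assign this category when no lesions can be measured is not advised".
- Section 12.4.4 on duration says: "Stable disease is measured from the start of the treatment until the criteria for progression are met".

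**What is counted.** Section 2.2 has the objective "To determine the clinical benefit rate (CR+PR+SD for at least 6 months", and an overall response rate of CR plus PR. No section maps Non-CR/non-PD to SD or to clinical benefit.

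**Who is in the denominator.** Section 5.2 states: "All patients are evaluable for disease response unless they discontinue treatment due to treatment related adverse events(s) prior to completion" of a first disease assessment. Section 15.2 plans the clinical benefit rate (CBR) on about 33 second-line and 14 first-line patients, which is all 47. Section 15.3 gives ORR and CBR with 95% confidence intervals, says analyses cover all patients and subgroups, and does not mention Section 5.2.

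**The concern.** The CBR is meant to capture durable absence of progression as well as shrinkage. The protocol deliberately admits patients whose disease cannot be measured, gives them their own response category for not progressing, and then leaves that category out of the endpoint. A patient with bone-only disease who is progression-free for a year would be a failure for CBR unless the analyst sets the protocol's footnote aside. Two analysts working from the same data could report different rates.

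The denominator question is separate and smaller. The patients whom Section 5.2 removes are those who could not tolerate treatment long enough to be scanned. That exclusion is related to outcome and would usually favour the regimen, in a trial whose purpose is to study tolerability.

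CBR is the only efficacy endpoint for which Section 15.2 gives planning precision, by line of therapy, so its numerator and denominator ought to be fixed before response data are analysed.

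**Working it through.** **Step 1: reproduce the plan's figures.** Inputs from Section 15.2: n = 33 at 67% (second line) and n = 14 at 84.3% (first line). Clopper-Pearson limits with x = n × p are the 0.025 quantile of Beta(x, n − x + 1) and the 0.975 quantile of Beta(x + 1, n − x).
- x = 33 × 0.67 = 22.11: 48.5% to 82.3%.
- x = 14 × 0.843 = 11.802: 55.5% to 97.7%.

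Both match Section 15.2, so no stated figure is wrong.

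**Step 2: routes to clinical benefit under Section 2.2.**

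| Disease at baseline | CR | PR | SD ≥ 6 months | Not progressing ≥ 6 months, no CR |
|---|---|---|---|---|
| Measurable | yes | yes | yes | covered by PR or SD |
| Non-measurable | yes | no row in 12.4.3 | no row; advised against | Non-CR/non-PD, not counted |

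**Step 3: size of the definition effect.** Let m be the share of patients with non-measurable disease only, and c the share of benefiting non-measurable patients who reach CR. Neither is in the documents; both are assumptions. Assume also that the true benefit rate p is the same in both groups. Then

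reported CBR = p × (1 − m × (1 − c)).

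| m | 2nd line, c = 0 | 2nd line, c = 20% | 1st line, c = 0 | 1st line, c = 20% |
|---|---|---|---|---|
| 10% | 60.3% | 61.6% | 75.9% | 77.6% |
| 20% | 53.6% | 56.3% | 67.4% | 70.8% |
| 30% | 46.9% | 50.9% | 59.0% | 64.1% |
| 40% | 40.2% | 45.6% | 50.6% | 57.3% |

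When does the expected rate fall below the plan's own lower limit, with c = 0?
- Second line: m > 1 − 0.485/0.67 = 27.6%, and 0.276 × 33 = 9.1. Nine patients give 0.67 × 24/33 = 48.7%, still above 48.5%. Ten give 0.67 × 23/33 = 46.7%. So 10 of 33 are needed.
- First line: m > 1 − 0.555/0.843 = 34.2%, and 0.342 × 14 = 4.8. Five patients give 0.843 × 9/14 = 54.2%, below 55.5%. So 5 of 14 are needed.

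**Step 4: size of the denominator effect.** Section 15.2 expects about 22 + 11 = 33 patients with benefit among 47: 33/47 = 70.2% (exact 95% CI 55.1% to 82.7%, 27.6 points wide). Section 1.2 gives two discontinuation rates as a guide to how many might be removed: 2.6% for any adverse event in PALOMA3 and 7% for treatment-related events in PALOMA1.
- 0.026 × 47 = 1.2, about 1 removed: 33/46 = 71.7% (56.5% to 84.0%), +1.5 points.
- 0.07 × 47 = 3.3, about 3 removed: 33/44 = 75.0% (59.7% to 86.8%), +4.8 points.

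These are upper guides. Both rates cover the whole treatment period, while Section 5.2 acts only before the first assessment, which the study calendar puts at the end of cycle 2 or 3 (about 8 to 12 weeks).

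**The case against.** **The footnote does not prohibit SD.** It states a preference and treats SD and Non-CR/non-PD as labels for much the same non-progressing state. Section 12.4.4 runs SD until progression criteria are met, and Section 15.2 plans CBR over all 47 patients, which makes little sense if CR were the only route for some of them. This stands as a reason why a sensible analyst might count these patients. It does not settle the matter: that reading requires doing what the footnote advises against, and no sentence authorises it.

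**A reader might infer that the comparison with 67% and 84.3% is biased.** The documents do not support that. They do not say how the source trials scored such patients. If those trials used the same rule, the rule would not distort the comparison. Section 15.2 also sets no test or decision rule against these figures; it gives precision only.

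**A reader might infer that Sections 5.2 and 15.3 contradict each other.** That is too strong. Section 5.2 is a specific rule and is most naturally read as governing response rates. The reference to all patients in Section 15.3 may only mean overall as opposed to subgroups, and the 33 and 14 are approximate planning numbers. What remains is a missing cross-reference and an outcome-related exclusion that could easily be avoided, with a small numerical effect.

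**PFS already credits these patients**, since Section 12.4.5 counts time to progression or death whatever the measurability. This is true, and it limits the damage, but it does not repair CBR.

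**Conclusion.** The CBR definition is wrong as written for an eligible group: a non-measurable patient who is progression-free for six months or more without CR is scored as no benefit. The size depends wholly on the unknown non-measurable share. Over an assumed 10% to 40%, with equal true benefit and no CRs, the expected rate drops by 6.7 to 26.8 points in second line (67% to between 60.3% and 40.2%) and by 8.4 to 33.7 points in first line (84.3% to between 75.9% and 50.6%). Some CRs would soften this.

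The denominator point is a cheap improvement rather than an error. Its effect of about 1.5 to 4.8 points is an upper guide and is small against an interval about 28 points wide.

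Overall severity is low to moderate. A reader might infer that the trial's main conclusion is at risk. It is not: the primary neutropenia test, N = 47 and the cut-off of 24 are untouched, and Section 5.2 keeps every treated patient evaluable for toxicity.

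**What to change.** **Sections 2.2 and 15.3:** define CBR as CR, PR, or either SD or Non-CR/non-PD lasting at least six months.

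**Sections 5.2 and 15.3:** make all patients who receive any study treatment, the set Section 5.2 already uses for toxicity, the primary denominator for ORR and CBR. Count patients with no response assessment as without response or benefit. Report the Section 5.2 evaluable set as a sensitivity analysis, and state how many patients were enrolled but never treated.

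**ORR:** non-measurable patients have no PR category, so an all-treated ORR gives them only CR as a route to response. Report ORR also in patients with measurable disease at baseline.

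**Cost:** a wording amendment with IRB review at the coordinating center and the secondary sites under Section 16.0, made before response data are analysed. No patients, visits or data are added. The denominator rule gives slightly less favourable rates, and Non-CR/non-PD is a less precise assessment than measured SD.
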